**4.12 Describe the process that you will employ to ensure the subjects are fully informed about this research study.**

\* Addressed below:

**This description must include the following elements:**

- who from the research team will be involved in the consent process (both the discussion and documentation);
- person who will provide consent or permission;
- information communicated; and
- any waiting period between informing the prospective participant about the study and obtaining consent

In addition, address the following if applicable based on your subject population:

- process for child assent and parental permission
  - continued participation if a child subject turns 18 during participation
- process for obtaining proxy consent and assent for decisionally impaired subjects
  - continued participation if subject regains capacity to consent

Drs. [name], [name], [name], or [name] will be involved in the consent process to discuss the study in detail with the parent including all of the potential risks. The consent form will be provided and the parent will be free to ask any questions related to the study. We will provide the parent with the option to sign the consent form at a later date if they choose to do so.

Legal guardians may provide consent only if they have a court order specifically indicating their authority.

**4.13 Are you requesting an exception to either IRB policy related to the informed consent process?**

- For studies involving a drug, device or surgical procedures, a *listed physician* investigator is required to obtain the written informed consent unless an exception to this policy has been approved by the IRB
- For all other studies, a *listed* investigator is required to obtain consent (Note: In order to request an exception to this policy, the study must be minimal risk)

\* No

If **Yes**, provide a justification and describe the qualifications of the individual who will obtain consent:

**4.14 Will you inform research subjects about the outcome of this research study following its completion?**

\* No

If **Yes**, describe the process to inform subjects of the results:

**5.1 Describe potential risks (physical, psychological, social, legal, economic or other) associated with screening procedures, research interventions/interactions, and follow-up/monitoring procedures performed specifically for this study:**

\*

View	Research Activity:	Electrical Stimulation of the Foot
	Common Risks:	Common risks may include potential foot cramp, skin irritation, redness, or rash.
	Infrequent Risks:	N/A
	Other Risks:	N/A
View	Research Activity:	Medical Record Review
	Common Risks:	No Value Entered
	Infrequent Risks:	No Value Entered
	Other Risks:	Potential for breach of confidentiality

**5.1.1 Describe the steps that will be taken to prevent or to minimize the severity of the potential risks:**

To minimize foot cramping, the lowest threshold voltage required (to induce spontaneous movement of the toes) will be used for actual stimulation. To minimize the risks, the research procedures will be conducted by experienced personnel. The subjects will be appropriately trained on how to use the TENS stimulator and attach the electrodes. The subjects will also be told that they can call the investigators anytime with any questions or problems.

**5.2 What steps will be taken in the event that a clinically significant, unexpected disease or condition is identified during the conduct of the study?**

\* **Addressed below:**

The study will be stopped immediately in the event that a clinically significant, unexpected condition is identified. The subject will also be referred to appropriate care for the unexpected condition.

**5.3 All the risk questions (screening, intervention/interaction, follow-up) have been merged into one question (5.1).**

[\[reviewer notes-\]](#)

**5.4 Do any of the research procedures pose a physical or clinically significant psychological risk to women who are or may be pregnant or to a fetus?**

\* No

[\[reviewer notes-\]](#)

**5.5 Do any of the research procedures pose a potential risk of causing genetic mutations that could lead to birth defects?**

\* No

[\[reviewer notes→\]](#)

**5.6 Are there any alternative procedures or courses of treatment which may be of benefit to the subject if they choose not to participate in this study?**

\* Not applicable

If **Yes**, describe in detail:

[\[reviewer notes→\]](#)

**5.7 Describe the specific endpoints (e.g., adverse reactions/events, failure to demonstrate effectiveness, disease progression) or other circumstances (e.g., subject's failure to follow study procedures) that will result in discontinuing a subject's participation?**

\* Describe below:

The study is expected to end when the six weeks have been completed with associated completion of weekly night-time voiding log and quality of life questionnaires. However, if the subject can not follow the study procedures such as an inability to tolerate foot stimulation or non-compliance with completing night-time voiding logs and/or quality of life questionnaires, the subject's participation will be discontinued and the study will be ended.

We expect some electrodes to detach from the foot. However, occasional unattached electrodes will not end the study, since the data will be collected in a week period and a few occurrences of detachment should not change the results. Also, if skin irritation is caused by the electrodes, the study will continue by using the other foot and giving the irritated foot a day or two to recover. However, if unexpected serious irritation occurs that cannot be avoided by changing feet, the study will be terminated for that subject.

[\[reviewer notes→\]](#)

**5.8 Will any individuals other than the investigators/research staff involved in the conduct of this research study and authorized representatives of the University Research Conduct and Compliance Office (RCCO) be permitted access to research data/documents (including medical record information) associated with the conduct of this research study?**

\* No

**5.9 Has or will a Federal Certificate of Confidentiality be obtained for this research study?**

\* No

**5.10 Question has been moved to 5.17****5.11 Question has been moved to 5.16**[\[reviewer notes~\]](#)**5.12 Does participation in this research study offer the potential for direct benefit to the research subjects?**

No - Describe the general benefits to society (e.g., increased knowledge; improved safety; better health; technological advancement) that may result from the conduct of this research study.

Describe the benefit:

The subject may not receive direct benefit from participation in this research study. Although the electrical stimulation may help with nocturnal enuresis, this benefit is not known or guaranteed. However, information learned from this study will help investigators learn how to better manage the conditions of nocturnal enuresis.

**5.13 Describe the data and safety monitoring plan associated with this study. If the research study involves multiple sites, the plan must address both a local and central review process.**

11. Drs. [name], [name] and [name] will be responsible for the data and safety monitoring.

2. After the ADDITIONAL 3 WEEKS OF ONGOING stimulation, parents will be called on the telephone by either [name] or [name] to inquire if any issues and assess the child's tolerability to continue treatments. All questions will be addressed as well. If no issues, the patient will continue the EXTENDED study and follow-up in clinic at the conclusion to submit their completed log and return the stimulation device. If during the monitoring telephone call an issue is detected, Drs. [name] or [name] will attempt to troubleshoot issues related to device usage over the telephone. A follow-up phone call will be scheduled on an as needed basis (2-3 days later) if any adjustments are made to the parents' technique of providing the stimulation or adjustments to the device settings. If at the monitoring phone call it is determined that the child is not reasonably tolerating the stimulation and/or they have developed concerning side effects, a prompt clinic appointment will be made to assess the child in person and remove them from the study.

3. The investigators will monitor the progress of the study and the efficacy of the treatment after collecting data from the first 10 subjects. Any unexpected adverse effect will be addressed immediately and reported to the IRB committee. In addition to the monitoring of every 10 subjects, an annual review of the study will also be conducted to assure the experimental design, identify any unexpected adverse effects for reporting, and review the progress of subject recruitment

4. The data will be locked in the urology office by the investigators for safety and privacy. An annual review of the safety and privacy of the data will be performed. If any problem occurs, it will also be addressed immediately during any time of the year.

5. The following will be reported to IRB annually: a list of persons who monitored the data

and safety; the date when the monitoring/review occurs; a summary of any problems detected; final decisions about changes of the study based on the annual review.

6. The potential adverse events may be reported to IRB including:

Use of TENS stimulator: Foot skin irritation, redness, or rash, or foot cramp.

[reviewer notes~]

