**Neuromodulation:**

In the office to calibrate TENS device - skin surface electrodes will be attached to the bottom of one foot for electrical stimulation. The stimulator and electrodes are FDA-approved devices for TRANSCUTANEOUS ELECTRICAL NERVE STIMULATION (TENS) and are commercially available. The stimulation characteristics include a continuous frequency of 5 Hz, pulsewidth 0.2 ms, and intensity 2-4 times the threshold voltage required for inducing

toe twitching - or the intensity that the subject feels comfortable with. The subjects will also be instructed how to use the stimulator and where to attach the electrodes on the foot at the beginning of the study. The investigator will provide the stimulator and electrodes. The subjects will be asked to wear socks to prevent the electrodes from detachment and to stop the stimulation during walking or in any non-resting situation. Subjects will be provided a TENS device and disposable foot pads for two weeks of treatment. Subjects will be asked to use the stimulator for a MINIMUM of 60 minutes in the evening prior to bedtime at home for two weeks. They will be encouraged to use the stimulator for more time than the minimum as long as they accurately record the total duration. Stimulation will be performed during the second and third weeks of the study only.

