#### Questionnaire:

Subjects will complete the quality of life questionnaire attached to this application at the start of the study (prior to week 1) to establish a baseline, after the second week of treatment period (week 4 of study) to determine a treatment effect, and after the sixth week to determine any residual post-treatment effect.

The subjects can call or email the investigators anytime during the 6-week at-home test for questions or any problems encountered. At the end of the 6-week study, the subjects are asked to return the stimulator and night-time voiding log to the investigator's office.

Subjects who feel they are having a positive response to TENS treatment and would like to continue participation in the study for an additional 6 weeks may do so. We will ask that they continue to keep their logs and answer the questionnaires

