**2.17 What are the main outcome variables that will be evaluated in this study?**

1) Number of night-time incontinent episodes per two week period comparing baseline number of voids (first two weeks of study), number during two-week stimulation period (weeks 3-4), and number during two-week after-stimulation period (weeks 5-6).

2) Subjective quality of life measures as recorded by validated quality of life questionnaire prior to study start, after week 4 and after week 6 to evaluate for any differences.

3) For the subjects who continue participation for an additional 6 weeks, we hope to prove long-term efficacy and sustainability in symptom relief, and to ensure no unanticipated adverse outcomes with continued usage

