**3.10 What is the total number of subjects to be studied at this site, including subjects to be screened for eligibility?**

Note: The number below is calculated by summing the data entered in question 3.11. Any additions or changes to the values entered in 3.11 will be reflected in 3.10.

\* 40

**3.11 Identify each of the disease or condition specific subgroups (include healthy volunteers, if applicable) that will be studied.**

Click on the "Add" button and specify for each subgroup:

1) how many subjects will undergo research related procedures at this site; and

2) if applicable, how many subjects will be required to undergo screening procedures (e.g., blood work, EKG, x-rays, etc.) to establish eligibility. **Do Not include subjects who will undergo preliminary telephone screening.**

\*

Subgroup	Number to undergo research procedures	Number to undergo screening procedures
View Pilot study of tibial nerve stimulation	25	40

**3.12 Provide a statistical justification for the total number of subjects to be enrolled into this research study at the multicenter sites or this site.**

\* Described below:

This is a pilot study to determine if foot stimulation has any effect on nocturnal enuresis. The study is designed through the use of an objective night-time voiding log and subjective quality of life questionnaires to determine the effect of foot stimulation. As the variations on these symptom parameters is unknown, it is difficult to to determine the total number of subjects based on statistical analysis. Therefore, we decided on 25 subjects in this pilot study. Once statistical significance is reached , we will stop recruiting additional subjects in order to maintain the subject number at a minimum.

[\[reviewer notes~\]](#)

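### No scheduled adverse-event question is described for the core two weeks of home stimulation; the only planned enquiry about problems falls inside the self-selected extension

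*Combined protocol and SAP*

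**What the plan says.** **Core phase.** Under 2.6 (Neuromodulation), "Subjects will be asked to use the stimulator for a MINIMUM of 60 minutes in the evening prior to bedtime at home for two weeks". The planned number is a choice, not a calculation: "Therefore, we decided on 25 subjects in this pilot study". It is a maximum, because section 3.12 adds "Once statistical significance is reached , we will stop recruiting additional subjects". The night-time log is described in 2.6 as a count of wet episodes, with time on the stimulator also to be recorded. The questionnaire is described as a quality-of-life measure. For problems, 2.6 offers an open line: "The subjects can call or email the investigators anytime during the 6-week at-home test for questions or any problems encountered". Section 2.7 answers in the negative when asked about research follow-up, a category it defines to include telephone calls.

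**Extension.** Entry is open to "Subjects who feel they are having a positive response to TENS treatment and would like to continue participation". Section 5.13 item 2 schedules a parental call: "After the ADDITIONAL 3 WEEKS OF ONGOING stimulation, parents will be called on the telephone". The next step shows which phase it belongs to: "If no issues, the patient will continue the EXTENDED study".

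**Safety intent.** Section 5.13 item 3 plans reviews after every 10 subjects and annually, the annual one partly to find unexpected adverse effects. Section 5.1 names foot cramp, skin irritation, redness and rash as common risks. Aim 3 in section 1.2 and outcome 3 in section 2.17 add the goal "to ensure no unanticipated adverse outcomes with continued usage".

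**The concern.** Solicited and spontaneous reports are different data. A family that is asked will mention a mild cramp or a red patch; many families that are not asked will say nothing. As written, the phase in which every child is first exposed at home has spontaneous reporting only. The one solicited enquiry goes to children who chose to continue because they felt better. A child bothered by the first two weeks is plausibly less likely to be among them.

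Two things are at stake. Mild events that the plan itself expects to be common are likely to be under-counted. And any tolerability statement from the pilot would rest on a denominator that is neither all treated children nor a random part of them. Section 2.2.2 classes the use as off-label, and the minimal-risk case in T3.1 and 3.5.5 leans on adult experience and on parasacral stimulation in children. How children tolerate stimulation of the foot at home is therefore something this pilot is placed to measure.

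**Working it through.** **Step 1: which provisions solicit adverse events, and from whom.**

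| Provision | Who is reached | Scheduled adverse-event question described? |
|---|---|---|
| 2.6, five-minute clinic test | All, before home use | No; a comfort check that decides eligibility |
| 2.6, night-time log | All | No; wet episodes, plus duration of use |
| 2.6, questionnaire | All | No; quality of life |
| 2.6 and 5.1.1, telephone or email | Families who choose to make contact | No; spontaneous |
| 2.6, device and log return at week 6 | All who complete | No question described |
| 5.7, stopping or changing feet | Children with a problem | No; no record of a change of feet is described |
| 5.13 item 2, telephone call | Extension only | Yes |
| 5.13 item 3, reviews | Data already held | No; adds no enquiry |

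The negative answer in 2.7 is consistent with this table but does not prove it alone, since the call in 5.13 also sits awkwardly with that answer. The argument rests on the absence of any described question in the core phase.

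**Step 2: scale.** The plan gives no event rate, safety precision or extension size, so there is no figure of its own to reproduce. Inputs: 25 children (3.12), and an assumed number of continuers m from 5 to 20.

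- Share never asked = (25 − m)/25.
- Zero-event one-sided 95% upper limit = 1 − 0.05^(1/n).
- Chance of seeing at least one event at true rate p = 1 − (1 − p)^n.

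| Children asked | Share of 25 never asked | Upper limit, zero events | At least one event, p = 5% | At least one event, p = 10% |
|---|---|---|---|---|
| 5 | 80% | 45.1% | 22.6% | 41.0% |
| 10 | 60% | 25.9% | 40.1% | 65.1% |
| 15 | 40% | 18.1% | 53.7% | 79.4% |
| 20 | 20% | 13.9% | 64.2% | 87.8% |
| 25 | 0% | 11.3% | 72.3% | 92.8% |

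For example, 1 − 0.05^(1/25) = 0.113 and 1 − 0.95^25 = 0.723. If recruitment stopped early, say at the review after 10 subjects, asking every child would give the row for 10.

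**Step 3: selection.** Sample size is the smaller part of the problem. As a constructed extreme, suppose 20 of 25 continue and the 5 who do not are exactly those who had cramp. The call then finds 0 of 20, with an upper limit of 13.9%, while the true frequency is 5/25 = 20%. The limit would exclude the truth. The documents do not say this will happen; it shows why limits computed in continuers cannot be read as limits for all treated children.

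**The case against.** The other side has real points.

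- **The core phase is not without safety provisions.** A reader might infer that it yields no safety data at all. The documents do not support that. Families can make contact at any time, 5.7 covers irritation and intolerance, 5.16 keeps and analyses data obtained before withdrawal, and 5.13 provides for immediate IRB reporting of unexpected effects. What is missing is a scheduled question.
- **The forms are not shown.** The log and survey are attachments. Neither is described as asking about adverse events, but an item on one of them cannot be ruled out.
- **Children are not sent home untested.** One might picture intolerant children having their first exposure at home. Those who cannot tolerate the five-minute clinic session are excluded (2.6, 3.14). Five minutes does not stand in for an hour or more nightly, but it removes the plainly intolerant.
- **The stated aim is narrower than it looks.** It is tempting to see a contradiction between the goal "to ensure no unanticipated adverse outcomes with continued usage" and the timing of the call. That goal is limited to continued use, and the call sits in the phase it concerns. The study-wide intent comes from 5.13 item 3.
- **The precision gain may be small.** A claim that asking everyone halves the uncertainty would depend on roughly 10 to 12 children continuing, which has no basis in the documents. With 20 continuers the comparison is 13.9% against 11.3%. A zero-event bound is also an imperfect yardstick for events expected to be common.
- **Filtering on tolerance is an inference.** The stated filter is perceived response and willingness to continue.

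These narrow the point. None supplies a scheduled adverse-event question for the core phase.

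**Conclusion.** The point holds in this form: as described, solicited information on problems and tolerability comes only from self-selected continuers, and core-phase events depend on spontaneous contact or withdrawal. This falls short of the study-wide intent in 5.13 item 3. It does not affect the two efficacy outcomes, and it does not show that the study is unsafe.

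The loss of information depends on the unstated extension size. Over an assumed 5 to 20 continuers, 80% to 20% of a full 25 would never be asked, and the zero-event upper limit would be 45.1% to 13.9% instead of 11.3%. The selection would remain even with many continuers. The conclusion assumes that the log and survey contain no adverse-event item and that 25, a maximum, is reached. If the forms already ask, the gap is only in the description.

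**What to change.** 1. If the forms already contain an adverse-event item, say so in 2.6 and 5.13. If not, add one short item for every child to the existing log or to the questionnaire given at the end of stimulation: skin irritation, redness or rash, cramp, discomfort, other, none. Ask it again when the device is returned. Duration of use is already to be recorded and needs no addition.
2. Tie the item to the end of the stimulation weeks. Section 2.6 (Neuromodulation) puts stimulation in study weeks two and three, whereas Aim 2 and 2.17 put it in weeks three and four; these must be reconciled. Bring the answer in 2.7 into line with whatever contacts are planned.
3. In 2.18, state that event frequencies will be reported with exact confidence limits over all children who received any home stimulation, including those who withdrew, with the extension shown separately.
4. In Aim 3 and outcome 3, state the goal as estimating the frequency of adverse events with continued use. No sample of this size can guarantee their absence.

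The cost is a slightly longer form and one question at a return that is already planned. No visit, procedure or change to treatment is needed.

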## Section 5 - Potential Risks and Benefits of Study Participation

- 5.14 What precautions will be used to ensure subject privacy is respected?** (e.g. the research intervention will be conducted in a private room; the collection of sensitive information about subjects is limited to the amount necessary to achieve the aims of the research, so that no unneeded sensitive information is being collected, drapes or other barriers will be used for subjects who are required to disrobe)

The initial instruction of the TENS device will be conducted in a private examination room in the urology clinic. The 6 to 12-week voiding diaries and quality of life questionnaires will be conducted by the subjects/parents at home without privacy concerns.

- 5.15 What precautions will be used to maintain the confidentiality of identifiable information?** (e.g., paper-based records will be kept in a secure location and only be accessible to personnel involved in the study, computer-based files will only be made available to personnel involved in the study through the use of access privileges and passwords, prior to access to any study-related information, personnel will be required to sign statements agreeing to protect the security and confidentiality of identifiable information, whenever feasible, identifiers will be removed from study-related information, precautions are in place to ensure the data is secure by using passwords and encryption, because the research involves web-based surveys, audio and/or video recordings of subjects will be transcribed and then destroyed to eliminate audible identification of subjects)

The subject's name will only be used for screening and scheduling purposes. Once the subject enters the experiment, an ID number will be assigned to each subject in place of his/her name and only the subject's age and gender will be recorded for privacy reasons. Subject name will not appear on data collection forms.

The information linking the ID number with the subject's name will be stored in a separate secure location during the study, and will be destroyed at the end of the study. We will not keep any document to link the subject's name to the ID number. After the study is finished, we will have consent forms with subjects names and data forms with ID numbers. Since the link between names and ID numbers are not kept, there will be no identifiable information that could be released. However, the data on papers will still be locked for safety reasons and the electronic data will be stored in password-protected, fire-walled computers.

- 5.16 If the subject withdraws from the study, describe what, if anything, will happen to the subject's research data or biological specimens.**

If a subject requests withdrawal or is withdrawn by the PI, no further data should be collected, but all data obtained prior to withdraw will be retained and analyzed for the study purposes.

- 5.17 Following the required data retention period, describe the procedures utilized to protect subject confidentiality.** (e.g., destruction of research records; removal of identifiers; destruction of linkage code information; secured long-term retention)

After the required data retention period, all data and subject information will be destroyed.

[\[reviewer notes-\]](#)

**6.1 Will research subjects or their insurance providers be charged for any of the procedures (e.g., screening procedures, research procedures, follow-up procedures) performed for the purpose of this research study?**

\*  
No

[\[reviewer notes-\]](#)

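### Section 5.16 ends all data collection on a child the PI withdraws, with no adverse-event exception, so the course of the event that led to removal is not recorded afterwards

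*Combined protocol and SAP*

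**What the plan says.** Section 5.16 sets one rule for every withdrawal: "If a subject requests withdrawal or is withdrawn by the PI, no further data should be collected". It adds that "all data obtained prior to withdraw will be retained and analyzed for the study purposes".

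Elsewhere the protocol foresees that the investigators will remove children because of harm or poor tolerance:

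- Section 5.7 lists "inability to tolerate foot stimulation" among the reasons for ending participation.
- Section 5.7 also says that "if unexpected serious irritation occurs that cannot be avoided by changing feet, the study will be terminated for that subject".
- Section 5.13, item 2, covers the monitoring telephone call in the extension. If at that call "it is determined that the child is not reasonably tolerating the stimulation and/or they have developed concerning side effects", then "a prompt clinic appointment will be made to assess the child in person and remove them from the study".

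On reporting, section 5.13, item 3, says: "Any unexpected adverse effect will be addressed immediately and reported to the IRB committee". Item 6 introduces the listed skin reactions and foot cramp with the words "The potential adverse events may be reported to IRB including". Section 5.2 provides for referral to care when an unexpected condition is found.

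**The concern.** A child removed by the PI for a safety reason may still have the rash, irritation or other effect on the day of removal. Read as written, 5.16 stops the study's record on that day.

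The device is used off-label in children (2.2.2.1). The third main outcome (2.17) includes checking that longer use brings no unforeseen harm. A child taken out because of harm is the case that says most about that outcome. The final report could state that the event happened and that the child was removed. It could not say how long the event lasted, whether it needed treatment or how it ended, if any of that fell after removal.

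The concern is limited to the study's safety record. It does not question the child's care, and it claims no bias in the voiding-log or quality-of-life results.

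**Working it through.** The protocol states no figure to reproduce, because this is a rule about data collection. The check has two parts: whether any other section supplies the missing exception, and how many children could be affected.

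**1. Sections read against 5.16**

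- **5.7, removal for intolerance or serious irritation.** It ends the child's participation. It does not provide for following the event to resolution.
- **5.13, item 2, extension only.** There is one clinic assessment, tied to the removal itself, and no later contact is specified. No equivalent visit is described for a child removed during the main six weeks.
- **5.13, item 3.** Unexpected effects are dealt with and reported to the IRB. Duration, treatment and outcome are not requested.
- **5.13, item 6.** Reporting of the listed, expected events is worded as permissive.
- **5.2.** Referral is clinical care, not study data.
- **2.7.** The question on follow-up procedures done for research is answered No.
- **2.6.** The instruments described are a log of night-time wetting episodes and a quality-of-life questionnaire. No adverse-event form is described for any child.
- **2.14.** The medical-record items to be retained are diagnosis, age, history and diagnostic work already done. They do not include the later course of a study event.
- **5.15.** The link between name and study ID is destroyed when the study ends. A later clinic note on how the event resolved could not then be matched to the study record, so collection has to be planned in advance.

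No available section makes an adverse-event exception to 5.16 or requires the course after removal to be recorded.

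**2. Size**

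Input: 25 children are to undergo study procedures (3.11, 3.12). The documents give no rate of adverse events or removals, so the number of harm-related removals, r, is an assumption. The share of children is r/25.

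| Assumed r | r/25 |
|---|---|
| 0 | 0% |
| 1 | 4% |
| 2 | 8% |
| 3 | 12% |

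In the extension the number of children, n, is at most 25, so each such removal is 1/n, or at least 4%.

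These shares are upper bounds for the assumed r. They count every harm-related removal as leaving an unrecorded course, and an event that has ended by the time of removal leaves none.

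**The case against.** The best case against the point has five parts.

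- **Reach of 5.16.** The section answers a form question about what happens to a withdrawn subject's data or specimens. Safety handling sits in 5.13, and item 3 there is not limited to children still enrolled. The investigators could record the course while dealing with the event, and 5.16 may never have been meant to stop that. This may well be the intent, but the text does not say so. Staff who follow it literally would stop, and item 3 does not ask for duration, treatment or outcome.
- **Few children, minor events.** Ordinary irritation is handled by switching feet (5.7). Tolerance is tested for five minutes in clinic before a child can enter (2.6, 3.14). The listed risks are cramp, irritation, redness and rash (5.1). Discomfort may simply end when the device is off. All of this stands, and it is why the impact is called modest. Section 5.7 nevertheless foresees serious irritation, and without outcomes the study cannot show that such events stayed minor.
- **The extension's aim is already served.** That aim concerns unforeseen harm, which item 3 requires to be reported, and a child removed after the monitoring call is seen in person. This narrows the gap to what happens after that visit. It does not close it.
- **A larger gap lies elsewhere.** No adverse-event form is described for children who stay in the study either. That is fair, and amending 5.16 does not cure it. It is a separate matter and does not weaken this change.
- **The consent form is not in the review copy.** It may already allow such follow-up. That cannot be checked here.

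**Conclusion.** The concern holds. Section 5.16 is a stated rule that, followed as written, leaves a poorer safety record for the children the investigators remove because of harm, and no available section corrects it. The loss is confined to the study's record of the triggering event after removal. Earlier data, clinical care and IRB reporting of unexpected effects are intact.

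The number of children affected is unknown. The 0% to 12% range rests on an assumed 0 to 3 removals among 25 and is illustrative. The change is worth making because it is cheap and bears on a stated safety outcome, not because large harm is expected. Confidence is medium, since the consent form could not be read and the intent of 5.16 may be narrower than its wording.

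**What to change.** Amend 5.16 to separate two situations.

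- **Removed by the investigators for safety or tolerability.** Stop stimulation and stop collecting efficacy data. With parental permission, follow the triggering event by telephone or at routine clinic contacts until it resolves or stabilises, and record its duration, treatment and outcome. Lifting the bar alone would not be enough, because no existing form asks for these items.
- **Family withdraws permission.** Keep the present rule that nothing further is collected.

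Bring the answer to 2.7 into line, since it now says there are no research follow-up procedures. Check the consent form first and amend it only if it does not already allow this contact.

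The cost is a short amendment and a few extra contacts with the families of children removed for harm.
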